7.2 NULL AND ALTERNATIVE HYPOTHESES

The following testing procedure will be used to evaluate the superiority for the primary endpoint for empagliflozin 25 and 10 mg doses against placebo at the level of $\alpha = 0.025$. The overall probability of type I error is therefore maintained at $\alpha = 0.05$ (two-sided).

The superiority of treatment with empagliflozin to placebo will be tested for HbA_{1c} change from baseline at Week 26, via the pairwise comparison of the two higher empagliflozin doses against placebo, at $\alpha = 0.025$ level. Both doses will be tested in parallel on the Full Analysis Set (FAS) for the efficacy analysis and on the modified Intention-to-Treat (mITT) set for the effectiveness analysis; see Section 7.3 for the analysis set definitions. Both analyses will test the same null hypothesis:

H_{0,0,1}: Mean change from baseline in HbA_{1c} (%) after 26 weeks in the empagliflozin 10 mg group = Mean change from baseline in HbA_{1c} (%) after 26 weeks in the placebo group

 $H_{0,0,2}$: Mean change from baseline in HbA_{1c} (%) after 26 weeks in the empagliflozin 25 mg group = Mean change from baseline in HbA_{1c} (%) after 26 weeks in the placebo group

Following testing of the null hypotheses $H_{0.0.1}$ and $H_{0.0.2}$ for both efficacy and effectiveness for HbA_{1c}, within each dose group (empagliflozin 10 and 25 mg) the remaining alpha will be unequally split for testing the superiority of empagliflozin 2.5 mg to placebo on the primary endpoint and for testing the superiority of the key secondary endpoints for the higher doses as detailed below.

One-fifth of the remaining alpha will be used for testing the superiority of empagliflozin 2.5 mg to placebo on the primary endpoint. The test will be done twosided. The null hypothesis is as follows:

 $H_{0.0.3}$: Mean change from baseline in HbA_{1c} (%) after 26 weeks in the empagliflozin 2.5 mg group= Mean change from baseline in HbA_{1c} (%) after 26 weeks in the placebo group

Depending on the success of the testing of $H_{0,0,1}$ and $H_{0,0,2}$, $H_{0,0,3}$ will be tested at the following alpha level $\alpha_{0,3}$:

- If either $H_{0,0,1}$ or $H_{0,0,2}$ is rejected at 0.025 level, then $\alpha_{0.3} = 1/5 \times 0.025 = 0.005$.
- If $H_{0.0.1}$ and $H_{0.0.2}$ are both rejected at 0.025 level, then $\alpha_{0.3} = 1/5 \times 0.025 + 1/5 \times 0.025 = 0.01$.

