Statistical parameters will be displayed to a defined number of decimal places as specified in the BI guideline "Reporting of Clinical Trials and Project Summaries" ([7](#)).

Tabulations of frequencies for categorical data will include all possible categories and will display the number of observations in a category as well as the percentage (%) relative to the respective treatment group (unless otherwise specified, all patients in the respective patient set whether they have non-missing values or not). Percentages will be rounded to one decimal place. The category missing will be displayed only if there are actually missing values.

Treatment comparison

In all specified statistical analyses, treatment comparisons will be made between each randomised Empagliflozin group (2.5, 10 and 25 mg) and placebo.

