7.4 PRIMARY ENDPOINT

7.4.1 Primary analysis

The primary endpoint in this trial is the change from baseline in HbA1c (%) at 26 weeks. Efficacy and effectiveness will be tested in a hierarchical manner.

The primary efficacy analysis will be performed on the FAS (OC). Patients will be assigned to the treatment they were randomised to. Only on-treatment HbA1c values will be included

in the primary analysis. Only data up to the Week 26 timepoint will be included. All randomised treatment groups will be included in the same analysis.

Mean changes from baseline in HbA1c after 26 weeks will be analysed using a restricted maximum likelihood-based repeated measures approach (MMRM analysis). Analyses will include the fixed categorical effects of treatment, pre-existing insulin therapy, week and treatment by week interaction, as well as the continuous, fixed covariates of baseline HbA1c, baseline eGFR and baseline HbA1c by week interaction. Patient will be included as random effect. An unstructured (co)variance structure will be used to model the within patient measurements.

If this analysis fails to converge, the following covariance structures will be tested: first-order ante-dependence (ANTE(1)), heterogeneous Toeplitz (TOEPH), Toeplitz (TOEP) and first-order autoregressive (AR(1)). The (co)variance structure converging to the best fit, as determined by Akaike's information criterion, will be used as the primary analysis.

The Kenward-Roger approximation will be used to estimate denominator degrees of freedom. Significance tests will be based on least-squares means using a two-sided $\alpha = 0.025$ (two-sided 97.5% confidence intervals). The residuals are assumed to have a multivariate normal distribution with zero means and covariance matrix as specified above. The primary treatment comparisons will be the contrasts between active treatments and placebo at Week 26.

The statistical model will be:

HbA1c change from baseline = overall mean + continuous baseline HbA1c + pre-existing insulin therapy + continuous baseline eGFR + treatment + week + baseline HbA1c by week interaction + treatment by week interaction + random error

If the null hypothesis is successfully rejected for the efficacy analysis, then an effectiveness analysis will be performed on the mITT (OC-AD), including both on- and off-treatment data. The model will be the same as the model for the efficacy analysis described above.

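### SAP 7.4.1 (like protocol 7.3.1.1) sets 0.025 and 97.5% intervals for the primary contrasts without excepting 2.5 mg, which protocol 7.2 tests only behind a gate at 0.005 or 0.01

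*SAP*

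**What the plan says.** **SAP 7.4.1.** The primary model contains every arm: "All randomised treatment groups will be included in the same analysis". One significance level is given, two-sided 0.025, with "two-sided 97.5% confidence intervals". The comparisons it covers follow: "The primary treatment comparisons will be the contrasts between active treatments and placebo at Week 26". SAP Section 7 confirms that 2.5 mg is among them: "treatment comparisons will be made between each randomised Empagliflozin group (2.5, 10 and 25 mg) and placebo". The effectiveness step in SAP 7.4.1 names no dose.

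**Protocol 7.2.** "One-fifth of the remaining alpha will be used for testing the superiority of empagliflozin 2.5 mg to placebo on the primary endpoint". That share is worked out as 0.005 when one higher dose is rejected and 0.01 when both are, two-sided. Table 7.2: 1 lets alpha leave a higher dose only after that dose has passed both the on-treatment (efficacy) and the all-data (effectiveness) analysis. Without that, later tests are exploratory.

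**Protocol 7.1, 7.3 and 7.7.** Sections 7.1 and 7.3 attach 0.025 to 10 mg and 25 mg. Section 7.7 calculates power for 2.5 mg at 1% and 0.5%.

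**Protocol 7.3.1.1.** This section has the same blanket 0.025 and 97.5% rule as the SAP. It refers only to the contrast between treatments, and it limits the effectiveness analysis to 10 mg and 25 mg.

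**SAP 3 and 4.** Section 3 bases the SAP on protocol Section 7. The visible part of Section 4 lists changes to the insulin-dose window, the back-up covariance structures and the imputation model. It lists none to the alpha levels.

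**The concern.** SAP 7.4.1 is the text from which the primary analysis would be programmed. For 2.5 mg it states a level and an interval that do not match protocol 7.2, and no visible text gives that dose any other interval level. Two things could follow. Someone working from SAP 7.4.1 alone could declare 2.5 mg significant at a p-value below 0.025. Even if the test is done correctly, the report could show a 97.5% interval that excludes zero beside a confirmatory test that failed. Protocol 4.1.3 includes the 2.5 mg arm to establish a minimal safe and effective dose, so its decision threshold should not be open to two readings.

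**Working it through.** **Inputs.** Protocol 7.7: difference 0.3% HbA1c, SD 0.9%, 225 per arm, alpha 0.025 for the higher doses and 0.01 or 0.005 for 2.5 mg. Protocol 7.2: one-fifth share. Allocation is 1:1:1:1, so contrasts against the shared placebo arm have correlation 0.5.

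**1. The plan's own figures.**
- Alpha for 2.5 mg: 1/5 × 0.025 = 0.005 with one higher dose rejected; 2 × 0.005 = 0.01 with both.
- Sample size for 90% power at 0.025 (two-sample t-test): 225 per arm, as stated.
- Power for 2.5 mg at 225 per arm (noncentral t): 82.8% at 0.01 and 76.2% at 0.005, against the stated 82% and 76%.

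The protocol's scheme and power section agree with each other. The blanket 0.025 is what does not fit.

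**2. Level.** 0.025/0.01 = 2.5 and 0.025/0.005 = 5. If neither higher dose passes both analyses, the 2.5 mg alpha is zero.

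**3. Interval.** Standard error = 0.9 × √(2/225) = 0.0849. Half-width = z × standard error.

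| Two-sided alpha | Interval | z | Half-width (% HbA1c) | Power at 0.3% |
|---|---|---|---|---|
| 0.025 | 97.5% | 2.241 | 0.190 | 90.0% |
| 0.01 | 99% | 2.576 | 0.219 | 82.8% |
| 0.005 | 99.5% | 2.807 | 0.238 | 76.2% |

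Width ratios: 2.241/2.576 = 0.870 (13% narrower) and 2.241/2.807 = 0.798 (20% narrower). An observed difference between 0.190 and 0.219 (alpha 0.01), or between 0.190 and 0.238 (alpha 0.005), gives a 97.5% interval excluding zero while the confirmatory test fails. At the assumed effect, the chance of landing there is 90.0 − 82.8 = about 7%, or 90.0 − 76.2 = about 14%. These chances do not condition on the gate.

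**4. Familywise error if SAP 7.4.1 is followed literally.**
- All three doses at 0.025, no gate, global null (simulation, 4 million draws): 6.5%, against 4.6% for the two higher doses alone. The Bonferroni bound for three is 3 × 0.025 = 7.5%.
- Gate kept, global null: a 2.5 mg rejection can occur only after a higher-dose rejection, which is already an error. The rate stays at 4.6% whatever level 2.5 mg uses.
- Gate kept, both higher doses truly effective and rejected: the levels still in play are 2.5 mg plus 4/5 × 0.025 = 0.02 for each dose's key secondary endpoints. Planned: 0.01 + 2 × 0.02 = 0.05. With 2.5 mg at 0.025: 0.025 + 0.04 = 0.065. These sums are upper bounds, not error rates.

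**The case against.** The strongest reply is that the confirmatory level is already fixed. The SAP assumes knowledge of the protocol, rests on its Section 7, and visibly declares no change to alpha. No document says that the 2.5 mg null hypothesis is rejected at p below 0.025. This stands. A reader might infer from SAP 7.4.1 that the sponsor moved 2.5 mg to 0.025; the documents do not support that.

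The blanket rule did not start in the SAP either. It is in protocol 7.3.1.1, and protocol 7.3 covers all doses in the primary efficacy analysis, so including the 2.5 mg contrast is not itself a departure. This also stands. But the SAP now makes the rule expressly cover all active treatments, and it no longer names the doses for the effectiveness step.

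A reader might also infer that the key secondary endpoints inherit 0.025 and 97.5% because SAP 7.5.1.2 to 7.5.1.4 follow the primary strategy. That wording introduces the MMRM and its terms; it does not carry over a level. The hypoglycaemia section (SAP 7.5.1.1) uses a negative binomial model and does not refer to the primary strategy. Protocol 7.2 gives all these endpoints their own levels.

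Finally, the protocol decides by tests and does not require an interval at each gatekept level, so a clearly labelled nominal interval would do. That is fair, but no such label is visible. Parts of the SAP are redacted and could restate the scheme; the visible text of 7.4.1 would still conflict with it.

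**Conclusion.** The inconsistency is real and should be reconciled. SAP 7.4.1 and protocol 7.3.1.1 state a level and interval that are wrong for 2.5 mg under protocol 7.2. Protocol 7.2 still governs the confirmatory test, so a liberal test is not shown.

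If SAP 7.4.1 were applied literally, 2.5 mg would be tested at 2.5 or 5 times its allotment. A reader might take the 6.5% familywise error as the consequence. Under the global null that figure requires dropping the gate as well, which no document does. With the gate kept, inflation from the level alone can arise only when a higher dose truly works.

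The interval mismatch remains even when the test is done correctly: 13% or 20% too narrow, with a contradictory display for observed differences from 0.190 up to 0.219 or 0.238. Those limits assume 225 per arm, SD 0.9 and an unadjusted comparison; the width ratios do not depend on the sample size or SD.

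**What to change.** In SAP 7.4.1:

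- Limit two-sided 0.025 and 97.5% intervals to 10 mg and 25 mg, for both efficacy and effectiveness.
- State that 2.5 mg is tested on on-treatment data at the α₀.₃ defined in protocol 7.2: 0.01 with a 99% interval if both higher doses pass both analyses, 0.005 with a 99.5% interval if one does, and exploratory otherwise. Alternatively, keep the 97.5% interval for 2.5 mg and label it nominal.
- Refer to protocol 7.2 for the key secondary levels, and label as nominal any interval not at the tested level.

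Note in the SAP that the blanket sentence in protocol 7.3.1.1 is to be read in the same way. The cost is a few sentences and the interval levels in the programs. Design, sample size and data collection are unaffected.

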7.4.2 Model diagnostics

In order to check the validity of assumptions used in the primary efficacy and effectiveness analysis models, model diagnostics will be performed as follows:

- Residuals from the primary model will be checked for normality using a Q-Q plot.
- Variance homogeneity across treatment groups, potential outliers and leverage points will be inspected using descriptive statistics and graphical methods.

These analyses will be reported in Section 16.1.9.2 of the trial report.

[REDACTED]

[REDACTED]

[REDACTED]

█ [REDACTED]

█ [REDACTED]

█ [REDACTED]

[figure not shown]
█ [REDACTED]

█ [REDACTED]

[REDACTED]

[REDACTED]

█ [REDACTED]

7.5 SECONDARY ENDPOINTS

7.5.1 Key secondary endpoints

7.5.1.1 Rate of symptomatic hypoglycaemic AEs with confirmed plasma glucose <54 mg/dL and/or severe hypoglycaemic events confirmed by adjudication

[figure not shown]
Confirmatory analysis

The analysis of the rate of symptomatic hypoglycaemic AEs with confirmed plasma glucose <54 mg/dL and/or severe hypoglycaemic events confirmed by adjudication will utilise a negative binomial model, with terms for treatment, continuous baseline rate, continuous baseline HbA1c, continuous baseline eGFR and pre-existing insulin therapy as fixed effects and log(time at risk) as an offset. The results will be presented as a rate per patient-year. This analysis will be performed on the FAS (OC).

The baseline rate of symptomatic hypoglycaemic AEs with confirmed plasma glucose < 54 mg/dL and/or severe hypoglycaemic events confirmed by adjudication will be calculated based on the event rate during the 4 weeks prior to randomisation, see [Section 6.7](#).

The analysis of the rate from Week 5 to Week 26 will include all on-treatment events from the start of Week 5 (Day 29) until one day after treatment stop date. This period will also define the time at risk.

The analysis of the rate from Week 1 to Week 26 will include all on-treatment events from the date of first study drug intake until one day after treatment stop date. This period will also define the time at risk.

[REDACTED]

7.5.1.2 Change from baseline in body weight (kg) after 26 weeks

Confirmatory analysis

The analysis of change from baseline in body weight after 26 weeks will follow the strategy for the primary endpoint, MMRM. The model will include the fixed categorical effects of treatment, pre-existing insulin therapy, week and treatment by week interaction, as well as the continuous, fixed covariates of baseline HbA1c, baseline eGFR, baseline body weight and baseline body weight by week interaction. This analysis will be performed on the FAS (OC), including all available on-treatment data up to the Week 26 timepoint.

A descriptive statistics table will present body weight (kg) and body weight change from baseline over time on the FAS (OC, OC-AD).

The treatment response over the treatment period will be illustrated on the FAS (OC) for each visit by plotting the adjusted means (SE) for change from baseline in body weight (kg) at each visit based on the MMRM model. A similar graphic will be created plotting the descriptive mean body weight (kg) at each visit using the FAS (OC).

[REDACTED]

7.5.1.3 Change from baseline in total daily insulin dose (U/kg) after 26 weeks

Confirmatory analysis

The analysis of change from baseline in total daily insulin dose after 26 weeks will follow the strategy for the primary endpoint, MMRM. The model will include the fixed categorical

effects of treatment, pre-existing insulin therapy, week and treatment by week interaction, as well as the continuous, fixed covariates of baseline HbA1c, baseline eGFR, baseline total daily insulin dose and baseline total daily insulin dose by week interaction. This analysis will be performed on the FAS (OC), including all available on-treatment data up to the Week 26 timepoint.

The baseline total daily insulin dose will be calculated based on the mean daily insulin requirement during the run-in period (Visit 5 to Visit 6). The total daily insulin dose will be calculated for each visit, based on the mean daily insulin requirement over the 14 days prior to the visit (excluding the day of the visit). If <4 days of valid insulin data is available, the visit value will be set to missing. The source data for the total daily insulin dose is the e-diary and this does not undergo a cleaning process. For data handling rules, see [Section 5.4.6](#).

A descriptive statistics table will present total daily insulin dose (U/kg), total daily insulin dose absolute change from baseline and total daily insulin dose relative change from baseline over time on the FAS (OC, OC-AD).

The treatment response over the treatment period will be illustrated on the FAS (OC) for each visit by plotting the adjusted means (SE) for change from baseline in total daily insulin dose (U/kg) at each visit based on the MMRM model. A similar graphic will be created plotting the descriptive mean total daily insulin dose (U/kg) at each visit using the FAS (OC).

7.5.1.4 Change from baseline in blood pressure after 26 weeks

Confirmatory analysis

The analysis of change from baseline in blood pressure after 26 weeks will follow the strategy for the primary endpoint, MMRM. The model will include the fixed categorical effects of treatment, pre-existing insulin therapy, week and treatment by week interaction, as well as the continuous, fixed covariates of baseline HbA1c, baseline eGFR, baseline blood pressure and baseline blood pressure by week interaction. This analysis will be performed on the FAS (OC), including all available on-treatment data up to the Week 26 timepoint.

A descriptive statistics table will present blood pressure (mmHg) and blood pressure change from baseline over time on the FAS (OC, OC-AD).

The treatment response over the treatment period will be illustrated on the FAS (OC) for each visit by plotting the adjusted means (SE) for change from baseline in blood pressure (mmHg) at each visit based on the MMRM model. A similar graphic will be created plotting the descriptive mean blood pressure (mmHg) at each visit using the FAS (OC).

All analyses will be performed separately for SBP and DBP.

[REDACTED]

[REDACTED]

[figure not shown]
- [REDACTED]
- [REDACTED]
- [REDACTED]
- [REDACTED]

[figure not shown]
[REDACTED]

[figure not shown]
7.5.2 (Other) Secondary endpoint

This section is not applicable as no secondary endpoints have been specified in the protocol.

[REDACTED]

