3.3.2 Inclusion criteria

- 1. Signed and dated written informed consent by the date of Visit 1 in accordance with Good Clinical Practice (GCP) and local legislation
- 2. Male or female patient receiving insulin for the treatment of documented diagnosis of T1DM for at least 1 year at the time of Visit 1
- 3. Fasting C-peptide value of < 0.7 ng/mL (0.23 nmol/L) at Visit 2 measured by the central laboratory

Proprietary confidential information © 2016 Boehringer Ingelheim International GmbH or one or more of its affiliated companies

- 4. Use of, and be willing, based on the Investigator's judgement, to continue throughout the duration of the trial, either:
 - MDI of insulin consisting of at least one basal insulin injection and at least three daily bolus injections OR
 - CSII of any insulin type, with at least 5 months experience of using CSII prior to Visit 1

For both MDI and CSII, the total daily insulin dose must be ≥ 0.3 U/kg and ≤ 1.5 U/kg at Visit 1

- 5. HbA_{1c} \geq 7.5% and \leq 10.0% at Visit 5 measured by the central laboratory, and provided that the patient's HbA_{1c} does not increase by \geq 0.5% between Visit 1 and Visit 5
- 6. Based on the Investigator's judgement patient must have a good understanding of his/her disease and how to manage it, and be willing and capable of performing the following study assessments (assessed at Visits 1-5 and just before randomisation):
 - patient-led management and adjustment of insulin therapy
 - reliable approach to insulin dose adjustment for meals, such as carbohydrate counting
 - reliable and regular home-based blood glucose monitoring
 - recognise the symptoms of DKA, and reliably monitor for ketones
 - implementation of an established "sick day" management regimen
- 7. Age \geq 18 years at Visit 1
- 8. Body Mass Index (BMI) of > 18.5 kg/m² at Visit 1
- 9. eGFR ≥ 30 mL/min/1.73 m² as calculated by the CKD-EPI formula, based on creatinine measured by the central laboratory at Visit 1
- 10. Women of child-bearing potential* must be ready and able to use highly effective methods of birth control per ICH M3 (R2) that result in a low failure rate of less than 1% per year when used consistently and correctly. Such methods should be used throughout the study and the patient must agree to periodic pregnancy testing during participation in the trial. A list of contraceptive methods meeting these criteria will be provided in the patient information

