5. VARIABLES AND THEIR ASSESSMENT

5.1 TRIAL ENDPOINTS

5.1.1 Primary endpoint

In this trial, the primary endpoint to assess efficacy is the change from baseline in HbA_{1c} (%) after 26 weeks. Throughout this CTP, the term "baseline" for HbA_{1c} refers to the last observation prior to the first intake of randomised trial medication.

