5.2.4 Systolic/diastolic blood pressure and pulse rate (vital signs)

SBP and DBP as well as pulse rate (electronically or by palpation, count for 1 minute) will be measured at the timepoints indicated in the Flow Chart with a calibrated electronic sphygmomanometer. The BP measurement should be performed three times at each timepoint and the mean value of the measurements will be analysed.

[figure not shown]
Initially, BP should be taken 3 times in both arms. The arm with the higher average pressure (systolic or – if equal – diastolic) should be used for subsequent measurements; if measurements for both arms are equal, the non-dominant arm should be chosen.

BP measurements should always be performed on the same arm and, if possible, by the same person and using the same device. The same method must be used throughout the trial for a given patient i.e. if a patient receives the first BP measurement for example with an electronic device, the same method and device should be used throughout the study for this patient.

After patients have rested quietly, in the seated position for at least 5 minutes, 3 BP measurements will be taken approximately 2 minutes apart. The seated pulse rate should be from the second BP reading.

BP measurements should be recorded to the nearest 1 mmHg.

[figure not shown]
BP should always be measured before any blood samples are taken.

Trial Protocol Version 2.0

Page 50 of 122

Proprietary confidential information © 2016 Boehringer Ingelheim International GmbH or one or more of its affiliated companies

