6.2.1.2 T1DM therapy optimisation period (Visits 2, 3 and 4T)

• Visit 2 should be done with the patient in a fasted state (i.e. no food or drink except water for 10 hours) (see Section 5.3.3)

Proprietary confidential information © 2016 Boehringer Ingelheim International GmbH or one or more of its affiliated companies

- •
- Visit 3T, if performed as a telephone visit, does not require attendance at the clinic. If performed as a clinic visit, Visit 3 does not need to be done with the patient in a fasted state (see Section 5.3.3)
- Visit 4T is a telephone visit and does not require attendance at the clinic
- Each visit should only be performed once it has been confirmed that the patient is eligible to progress to the next visit; ineligible patients should be registered in the IRT system and the eCRF as a screen failure and no further follow-up is required
- BP should always be measured before any blood samples are taken (relevant for Visit 2 only). For details regarding the correct method for measuring BP, see Section 5.2.4
- At the end of each visit, patients should be reminded about the importance of entering
 data into their e-diary on a daily basis, including data from the glucose/ketone meter, so
 that optimisation of the T1DM therapy can be monitored remotely by designated sitepersonnel, and an assessment made of the need for weekly telephone discussions and/or
 additional visits

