6.2.1.3 Placebo run-in period (Visit 5)

- Visit 5 does not need to be done with the patient in a fasted state (see Section 5.3.3)
- Visit 5 should only be performed once it has been confirmed that the patient is eligible to progress to this visit, based on an assessment of results from Visits 2 to 4T
- As for Visit 1, BP should always be measured before any blood samples are taken. For details regarding the correct method for measuring BP, see Section 5.2.4
- Following completion of the Visit 5 procedures, eligible patients will be dispensed a placebo run-in kit for the 2 week run-in period which will be assigned via the IRT system. Ineligible patients should be registered in the IRT system and the eCRF as a screen failure and no further follow-up is required

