6.7 BASELINE, TIME WINDOW, AND CALCULATED VISITS

With regard to efficacy and safety endpoints, the term "baseline" refers to the last observed measurement prior to administration of any randomised study medication. For specific endpoints, baseline definitions are as follows:

Serum beta-hydroxybutyrate (BHB)

- Serum BHB sampled at the site and analysed at the central laboratory

Baseline will be defined as the fasted measurement observed at Visit 6, before first drug intake.

- Capillary patient self-measured BHB via the ketone meter and reported in the diary

For the analysis on morning or daily measurements (see [Section 7.8.2.5](#)), baseline will be defined as the mean of morning or daily measurements reported during the run-in period, respectively (Visit 5 to Visit 6, including the day of first administration of trial drug).

[REDACTED]

Hypoglycaemia rate

The event rate of hypoglycaemia (using the respective endpoint definition) during the 4 weeks prior to randomisation (from Day -28 up to Day -1). Collapsing will be performed as per the rules in Sections [5.4.6.3](#) and [5.4.7](#). Rates will be presented per 30 days and also per patient year.

Insulin dose (total daily, total daily basal or total daily bolus)

Mean daily insulin requirement during the run-in period (Visit 5 to Visit 6, excluding day of randomisation). If < 4 days of valid insulin data is reported during the run-in period then the measurement will be considered missing. For data handling rules see [Section 5.4.6.2](#).

[REDACTED]

[REDACTED]

[REDACTED]

[REDACTED]

[REDACTED]

Table 6.7: 1 Endpoint specific follow-up period for the assignment to active treatment

Endpoint	Last day of assignment to treatment phase (days after study drug stop date)
Efficacy	
HbA _{1c}	7
FPG	1
MDG	1
CGM	*
Body weight	1
Blood pressure	1
Waist circumference	7
Insulin dose	0
Hypoglycaemia	1
UACR	1
Health economics and QoL	1
Safety	
Adverse events	7
Hypoglycaemia ^[1]	1
Hepatic injury ^[2]	30
Safety laboratory measurements	3
AST/ALT/TBL ^[3]	30
Pulse rate	1

*Refer to [Section 5.4.4](#) for the assignment of CGM measurements to the on-treatment period

[1] Refer to all hypoglycaemia analyses except the general hypoglycaemia AE analysis by SOC and PT.

[2] Refer to a sensitivity analysis including all hepatic injuries with an onset date up to 30 days after the study treatment stop (see Section 7.8.1.4).

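### The confirmatory SBP and DBP models adjust only for the last pre-dose reading; adding the Visit 5 reading already collected would gain a little precision at almost no cost

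*SAP*

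**What the plan says.** SAP 7.5.1.4 gives the confirmatory SBP and DBP model as an MMRM with treatment, pre-existing insulin therapy, week and treatment by week, together with "the continuous, fixed covariates of baseline HbA1c, baseline eGFR, baseline blood pressure and baseline blood pressure by week interaction". Protocol 7.3.2.1 specifies the same own-endpoint terms. SAP 6.7 says that baseline "refers to the last observed measurement prior to administration of any randomised study medication".

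The protocol Flow Chart schedules vital signs before randomisation at Visits 1, 2, 5 and 6, and at Visit 3 if it is held in the clinic. The visit sections agree. Protocol 6.2.1.2 says "BP should always be measured before any blood samples are taken (relevant for Visit 2 only"; Protocol 6.2.1.3, for Visit 5, says "As for Visit 1, BP should always be measured before any blood samples are taken". Protocol 5.2.4 adds: "The BP measurement should be performed three times at each timepoint and the mean value of the measurements will be analysed".

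Parts of SAP 7.5.1.4 are redacted, but the confirmatory model is printed in full. It contains no pre-dose blood pressure other than the baseline value.

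**The concern.** Blood pressure varies from visit to visit. Averaging three readings at one visit reduces measurement noise within that visit but not the variation between visits, so one visit is an imperfect measure of a patient's usual level. A second pre-randomisation visit carries further information about the Week 26 value, and that information is already scheduled to be collected.

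The plan accepts this idea elsewhere: SAP 6.7 takes baseline insulin dose as a run-in mean and the baseline hypoglycaemia rate over four weeks.

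SBP and then DBP come last in each dose's testing sequence, and Protocol 7.7 powers only HbA1c. Under some outcomes of the earlier tests they receive a very small alpha, where power is limited.

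**Working it through.** **The plan's own figures.** Blood pressure has no stated power, so only the alpha split and the HbA1c calculation can be reproduced.

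- Weight/TDID branch, dose's own primary null rejected, 2.5 mg null not rejected: 1/10 × 4/5 × 0.025 = 0.002, as in Protocol 7.2.
- HbA1c (Protocol 7.7): 0.3 / (0.9 × √(2/225)) = 3.536. Subtracting the two-sided 0.025 critical value, 2.241, gives 1.294, so power is 90.2% (90.05% by the t distribution). The stated 90% reproduces.

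**Alpha that SBP and DBP can receive when the dose's own primary null is rejected (Protocol 7.2)**

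| Branches that succeed | Alpha |
|---|---|
| Weight and TDID only | 0.002 to 0.0025 |
| Hypoglycaemia only | 0.018 to 0.0225 |
| Both | 0.02 to 0.025 |

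Protocol 7.2 also writes 1/10 × 1/2 × 0.005 = 0.00025 for body weight when the dose's own primary null is not rejected but those for the other high dose and 2.5 mg are. The same section's stopping rule, and Steps 1 and 2 of Table 7.2: 1, make later tests for that dose exploratory.

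**Assumed inputs for SBP (not in the documents).** Between-patient SD 12 and visit-to-visit SD 8 mmHg, true effect 3 mmHg, 225 per arm with complete data, other covariates ignored. With week interactions, the Week 26 contrast then behaves like an ANCOVA at Week 26.

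**Model A: the true level is equally correlated (ρ) with Week 26 from every pre-dose visit.** With m pre-dose visits, the residual variance is

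V = 12² + 8² − (ρ × 12²)² / (12² + 8²/m).

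For ρ = 0.8: m = 1 gives 208 − 13,271/208 = 144.2; m = 2 gives 208 − 13,271/176 = 132.6. The cut is 8.0%.

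**Model B: the true-level correlation decays exponentially with time.** It equals r over 26 weeks, hence r^(d/26) over d weeks. Visits 2, 5 and 6 stand at Weeks −8, −2 and 0. V = 208 − c′S⁻¹c, where S is the covariance matrix of the pre-dose readings and c holds their covariances with Week 26.

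For r = 0.8 with Visits 5 and 6: c = (115.2, 113.2), and S has 208 on the diagonal and 141.6 off it. This gives V = 133.3 against 144.2, a cut of 7.5%.

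**Power** = Φ(3/√(2V/225) − z), with z the two-sided critical value.

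| Model | Variance cut, Visit 5 | Variance cut, Visits 5 and 2 | Power at 0.0025: planned / +V5 / +V5 and V2 | Power at 0.02: planned / +V5 / +V5 and V2 |
|---|---|---|---|---|
| B, r = 0.6 | 3.3% | 4.1% | 27.5 / 28.9 / 29.2 | 53.9 / 55.6 / 56.0 |
| B, r = 0.7 | 5.0% | 6.4% | 30.8 / 33.2 / 33.9 | 57.8 / 60.3 / 61.1 |
| B, r = 0.8 | 7.5% | 10.0% | 35.4 / 39.5 / 40.9 | 62.7 / 66.6 / 68.0 |
| B, r = 0.9 | 11.2% | 15.3% | 42.0 / 48.8 / 51.7 | 69.0 / 74.8 / 77.0 |
| A, ρ = 0.8 | 8.0% | 11.4% | 35.4 / 39.7 / 41.8 | 62.7 / 66.9 / 68.8 |
| A, ρ = 0.9 | 11.5% | 16.4% | 42.0 / 49.0 / 52.4 | 69.0 / 74.9 / 77.6 |
| A, ρ = 1.0 | 16.7% | 23.8% | 51.4 / 62.8 / 68.4 | 76.8 / 84.7 / 88.0 |

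Visit 5 alone supplies 70% or more of the two-visit variance cut in every row.

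**Effect size matters too.** With residual SD 10 and alpha 0.002, a 10% variance cut moves power from 16.6 to 19.7% for a 2 mmHg effect, from 53.7 to 60.4% for 3 mmHg and from 87.5 to 91.6% for 4 mmHg.

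**HbA1c for comparison.** With an assumed Visit 5 to Visit 6 correlation of 0.90 to 0.97, adding Visit 5 cuts variance by about 0 to 5%. Even a 5% cut moves power only from 90.2 to 91.7%.

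**The case against.** The strongest reply is that nothing here is wrong. A single-baseline MMRM is pre-specified in both documents, is unbiased and controls type I error. That stands: this is an efficiency suggestion.

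The size is assumed. The only SBP effect in the documents is a type 2 diabetes figure of up to 4.8 mmHg (Protocol 1.2.3.1), and the 8 mmHg visit-to-visit SD has no source there. Simulating from the same model would confirm the algebra, not the size. This also stands, so only ranges are given.

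The extra visits are less comparable. Visit 5 is non-fasting whereas Visits 6 and 11 EOT are fasting, and Visit 2 precedes the six-week optimisation of diabetes therapy. This can shrink the gain but cannot bias a randomised comparison. It is why Visit 2 is only optional.

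A reader might infer more than the documents support:

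- **A variance loss near 24%, with power rising from 51 to 68%.** This needs both extra visits and no drift in a patient's true level up to Week 26. With decay, both visits give 4 to 15%.
- **Testing at 0.002 as the normal case.** It applies only when the weight/TDID branch alone succeeds; the other routes give 0.018 to 0.025. Nor is it the lowest written level, which is 0.00025. A small alpha lowers power; it does not change precision.
- **The same remedy for the primary endpoint.** The HbA1c model, with "baseline HbA1c, baseline eGFR and baseline HbA1c by week interaction", is built alike, and an HbA1c value is available "at Visit 5 measured by the central laboratory". But Protocol 3.2 describes HbA1c as reflecting the preceding 12 weeks. Visits 5 and 6, two weeks apart, share about 10 of them, and the test already has 90% power.
- **The same remedy for body weight.** No size has been established, and Protocol 5.2.2 asks for fasting weight only at fasting visits, so the Visit 5 weight is taken under different conditions.

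**Conclusion.** The point holds as a modest, optional gain for SBP and DBP only. Under the stated assumptions, Visit 5 cuts the variance of the Week 26 SBP contrast by about 3 to 17%, worth about 1 to 11 power points at alpha 0.0025 and 2 to 8 at 0.02. Adding Visit 2 as well gives about 4 to 24%, worth 2 to 17 and 2 to 11 points.

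The lower ends come from decaying correlation and the upper ends from a constant true level. The documents cannot say which is closer. No separate figures were worked out for DBP; the structure is the same but the size is unknown.

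The estimand does not change. With Visit 6 blood pressure and its week interaction in the model, the treatment contrast is the same whether or not baseline is subtracted, and the added covariate is measured before randomisation.

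**What to change.** In SAP 7.5.1.4, add Visit 5 SBP (DBP in the DBP model) as a continuous covariate with its week interaction. Visit 2 may be added in the same way. Keep change from the Visit 6 baseline as the endpoint. Where the extra reading is missing, substitute the patient's Visit 6 value so that nobody is lost.

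Protocol 7.3.2.1 states the blood pressure model, so list the change in SAP Section 4 and finalise it before unblinding. Leave the HbA1c and body weight models as they are.

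The cost is SAP text and a few degrees of freedom. Blood pressure has five post-baseline visits (Weeks 1, 4, 12, 18 and 26), so one covariate with its week interaction adds 1 + 4 = 5 parameters. No new data are needed.

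Separately, reconcile the 0.00025 route in Protocol 7.2 with the stopping rule in the same section and Table 7.2: 1, so that the alpha passed to SBP and DBP is unambiguous.
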